## **12.5 Reporting and Exclusions**

12.5.1 Evaluation of toxicity – All patients will be evaluable for toxicity from the time of their first treatment with lapatinib.

12.5.2 Evaluation of response – All patients included in the treatment portion of the study must be assessed for response to treatment, even if there are major protocol treatment deviations or if they are ineligible. Each patient will be assigned one of the following categories: 1) complete response, 2) partial response, 3) stable disease, 4) progressive disease, 5) early death from malignant disease, 6) early death from toxicity, 7) early death because of other cause, or 9) unknown (not assessable, insufficient data). [Note: By arbitrary convention, category 9 usually designates the “unknown” status of any type of data in a clinical database.]

All of the patients who met the eligibility criteria (with the possible exception of those who received no study medication) should be included in the main analysis of the response rate. Patients in response categories 4-9 should be considered to have a treatment failure (disease progression). Thus, an incorrect treatment schedule or drug administration does not result in exclusion from the analysis of the response rate. Precise definitions for categories 4-9 will be protocol specific. All conclusions should be based on all eligible patients. Subanalyses may then be performed on the basis of a subset of patients, excluding those for whom major protocol deviations have been identified (e.g., early death due to other reasons, early discontinuation of treatment, major protocol violations, etc.). However, these subanalyses may not serve as the basis for drawing conclusions concerning treatment efficacy, and the reasons for excluding patients from the analysis should be clearly reported.

## 13. HUMAN SUBJECTS PROTECTION

### 13.1 Rationale for Subjects Protection

- Selection based on gender, ethnicity, and race: Subjects from both genders and all racial/ethnic groups are eligible for this study if they meet the eligibility criteria. To date, there is no information which suggests that differences in drug metabolism or disease response would be expected in any one patient group. Efforts will be made to extend accrual to a representative population, but in this preliminary study, a balance must be struck between patient safety considerations and limitations on the number of patients exposed to potentially toxic treatments on the one hand and the need to explore gender and ethnic aspects of clinical research on the other. Prior toxicologic and clinical evaluations have not specifically assessed effects on juvenile animals. Therefore, this study will not include patients < 18 years of age. This is a Phase II trial designed to define the response rate, characterize the side effect profile, and assess several biological endpoints.

### 13.2 Evaluation of Benefits and Risks/Discomforts

Potential benefits to subjects expected from the trial: As a result of participating in this trial, patients will receive evaluation and treatment of their tumor. This protocol may or may not be helpful for a specific patient, but the results may help the investigators learn about the administration of lapatinib on a continuing basis. The

potential for this research treatment to offer control of the disease is unknown; however, based on information to date, the possibility of an effect on the progression of disease exists. Benefit cannot be promised nor can the chance of benefit be accurately predicted.

### **13.3 Consent and Assent Processes and Documents**

The investigational nature and objectives of this trial, the procedures and treatments involved and their attendant risks and discomforts, potential benefits and potential alternative therapies will be carefully explained to the patient or the patient's surrogate, and a signed informed consent document will be obtained by the PI, AI or clinical staff fellow. Moreover, any experimental invasive procedure will require a separate consent form.

## APPENDIX A: CLINICAL TRIALS OF LAPATINIB IN BREAST CANCER

### Clinical Trials of Lapatinib in Patients with Advanced or Metastatic Breast Cancera

Authors	Patient Population	No.	Treatment Regimens	Response
Burstein et al.[73] Phase II International OL	Cohort A: HER2-positive MBC refractory to an anthracycline, a taxane, capacitabine, and trastuzumab	140	Lapatinib 1,500 mg QD	Response RR: 4.3%; clinical benefit: 5.7%; median TTP: 9.1 wk; median PFS: 9.1 wk; median survival: 29.4 wk
	Cohort B: HER2-negative MBC refractory to an anthracycline, a taxane, and capecitabine	89		No objective responses; median TTP: 7.6 wk; median PFS: 7.6 wk; median survival: 18.6 wk
Blackwell et al.[74] Phase II MC, OL	HER2-positive MBC refractory to trastuzumab	78	Lapatinib 1,500mg QD	PR: 7.7%; clinical benefit: 21.8%
Iwata et al.[75] Phase II MC, OL	HER2-positive MBC refractory to an anthracycline, a taxane, capecitabine, and trastuzumab	45	Lapatinib 1,500mg QD	Clinical benefit: 33.3%
Gomez et al.[76] Phase II MC, R, OL	First-line treatment of HER2-positive advanced breast cancer or MBC	138	Lapatinib 1,500mg QD (n=69) or Lapatinib 500mg BID (n=69)	RR: 24%; clinical benefit: 31%; PFS at 6 mo: 43%; no difference in clinical activity between doses
Geyer et al.[77] and Cameron et al.[78] Phase III MC, R, OL	HER2-positive locally advanced breast cancer or MBC that had progressed with regimens including an anthracycline, a taxane, and trastuzumab	399	Lapatinib 1,250mg QD + capacitabine 1,000 mg/m  PO BID on days 1-14 of a 21-day cycle or Capacitabine 1,250mg/m  PO BID on days 1-14 of a 21-day cycle	Median TTP: 6.2 mo (combination) vs 4.3 mo (capacitabine alone) (HR=0.57; 95% CI, 0.43-0.77; p<0.001); improved PFS with combination vs capacitabine alone (HR=0.55; 95% CI, 0.4-0.74; p<0.001)
DiLeo et al.[79] Phase III MC, R, DB, PC	First-line therapy of HER2-negative or unknown advanced breast cancer or MBC	580	Lapatinib 1,500mg QD + paclitaxel 175mg/m  IV q3wk or Placebo + paclitaxel 175mg/m  IV q3wk	RR: 35.1% vs 25.3%, combination vs paclitaxel monotherapy, respectively (p=0.008); clinical benefit: 40.5% vs 31.9% (p=0.025); no difference in TTP or OS

afrom Medina PJ, Goodin S. Clin Ther 2008

## APPENDIX B: ERBB4 PRIMERS

GENE	Exon	Primer Name	Non M13 tagged Forward Primer	Primer Name	Non M13 tagged Reverse Primer
ERBB4	1b	ERBB4-X1b-F	GGGGATATGCCATTGGAC	ERBB4-X1b-R	CGGAGTGCCAGAAGGAAC
ERBB4	2	ERBB4-X2-F	AGAACTGGGATAGGCTTGTGG	ERBB4-X2-R	TTCCAGGTATCAGCACACAGG
ERBB4	3b	ERBB4-X3b-F	GGCAACTGTTGTGCTTTCA	ERBB4-X3b-R	AAGCATATTGCCATTGGAA
ERBB4	4b	ERBB4-X4b-F	TTCATCAACAAGCAGTTGACA	ERBB4-X4b-R	TCGCCACATAGGGTAGAACAA
ERBB4	5	ERBB4-X5-F	AAATCCTCATAAAGGAGCAGGAG	ERBB4-X5-R	CCAAAGCAAATCAACCACAAG
ERBB4	6	ERBB4-X6-F	TGAATTGAGTCAAAGACAGGGTG	ERBB4-X6-R	GGAATGACTTGAGGAGGGC
ERBB4	7b	ERBB4-X7b-F	TGAAAGTAATATTGCTGTGTTGC	ERBB4-X7b-R	TTCTTTGATTCAAATAATGACCT
ERBB4	8b	ERBB4-X8b-F	TGTTTGAGCTTGTTGCTGA	ERBB4-X8b-R	AAACCTTGTATAGGCCAGTTC
ERBB4	9b	ERBB4-X9b-F	TTGCCAAAAATAAGTTCTCAA	ERBB4-X9b-R	CACTTGAAAATAACTGCACAAAAAA
ERBB4	10b	ERBB4-X10b-F	AAATTGGCTACATCTCTCTGA	ERBB4-X10b-R	AAATTATATTGTTCATAGCGCAACA
ERBB4	11	ERBB4-X11-F	CCTTCTCACTCCCCAACCTTC	ERBB4-X11-R	TACCTCACACCATCATCGGAG
ERBB4	12b	ERBB4-X12b-F	TTTCTCACTCCCCCTCCT	ERBB4-X12b-R	TCCAAAGAAGAATGGGAAAAAA
ERBB4	13b	ERBB4-X13b-F	TCCCCCTGATTTGGTGT	ERBB4-X13b-R	ATGAGGTGAAGGCAACCTA
ERBB4	14	ERBB4-X14-F	TGATGCTCCTGGCACATAGAG	ERBB4-X14-R	CCCATGGCATCCTGTAAGTAG
ERBB4	15	ERBB4-X15-F	TCTTAGAGGAAGATTGCCACC	ERBB4-X15-R	CATTCAGAGATGGTACCAAGGG
ERBB4	16	ERBB4-X16-F	GCTTCCCATGTTCTCCTCC	ERBB4-X16-R	AAGTAAGAAAGTTGGCTTGAGAAGG
ERBB4	17	ERBB4-X17-F	TGTGGATAATGTCCTGTACAAC	ERBB4-X17-R	TTCACAAGCTTGTAAACGGAC
ERBB4	18b	ERBB4-X18b-F	TTCTTCTTCCGTTGCAG	ERBB4-X18b-R	TCCATTGGCTATTATTTCTAAACA
ERBB4	19b	ERBB4-X19b-F	TGTAACAGGTGCTAAATAAACATTG	ERBB4-X19b-R	TGATTGCCTGGGTGCTGTA
ERBB4	20b	ERBB4-X20b-F	TTGAGTTGAAATCATGGTATTGC	ERBB4-X20b-R	TTCCATAGAAATTGACAGGCACT
ERBB4	21b	ERBB4-X21b-F	GGGAAACCTGGGCATTAAC	ERBB4-X21b-R	TCAAGCAAGATTGCTCTCAAAA
ERBB4	22	ERBB4-X22-F	AGGCCAGCCAAAGACTC	ERBB4-X22-R	TAAC TGTTAGGAAATTAGGCTTATC
ERBB4	23b	ERBB4-X23b-F	TTGGTGTGGATTGACCTG	ERBB4-X23b-R	TGATGGTGATAACATTATTTGCAG
ERBB4	24	ERBB4-X24-F	GAGTCGTTCTTCACTAGCTTGC	ERBB4-X24-R	TGTTGTGGCTTCCACAG
ERBB4	25b	ERBB4-X25b-F	TGTGCTGATGGCAATCTT	ERBB4-X25b-R	TTATTTGAAATGTTAGTGCTTATGAA
ERBB4	26b	ERBB4-X26b-F	CCATCATTCCATTTCCTTCC	ERBB4-X26b-R	AAGCAAAGACCGAAAATCCT
ERBB4	27b	ERBB4-X27b-F	ACAAACGCCCTCTCCACAT	ERBB4-X27b-R	AATGGCGATCGTTCTGAAT
ERBB4	28_1b	ERBB4-X28_1b-F	TTTCAGAAACTAGAGGTTAGCTG	ERBB4-X28_1b-R	GGTAGTCTGGGTGCTGAAGG
ERBB4	28_2b	ERBB4-X28_2b-F	AGGCCGAGGATGAGTATGTG	ERBB4-X28_2b-R	GGAAATTGGAGCAGGTGTGT

## APPENDIX C: PERFORMANCE STATUS CRITERIA

ECOG Performance Status Scale		Karnofsky Performance Scale	
Grade	Descriptions	Percent	Description
0	Normal activity. Fully active, able to carry on all pre-disease performance without restriction.	100	Normal, no complaints, no evidence of disease.
		90	Able to carry on normal activity; minor signs or symptoms of disease.
1	Symptoms, but ambulatory. Restricted in physically strenuous activity, but ambulatory and able to carry out work of a light or sedentary nature (e.g., light housework, office work).	80	Normal activity with effort; some signs or symptoms of disease.
		70	Cares for self, unable to carry on normal activity or to do active work.
2	In bed <50% of the time. Ambulatory and capable of all self-care, but unable to carry out any work activities. Up and about more than 50% of waking hours.	60	Requires occasional assistance, but is able to care for most of his/her needs.
		50	Requires considerable assistance and frequent medical care.
3	In bed >50% of the time. Capable of only limited self-care, confined to bed or chair more than 50% of waking hours.	40	Disabled, requires special care and assistance.
		30	Severely disabled, hospitalization indicated. Death not imminent.
4	100% bedridden. Completely disabled. Cannot carry on any self-care. Totally confined to bed or chair.	20	Very sick, hospitalization indicated. Death not imminent.
		10	Moribund, fatal processes progressing rapidly.
5	Dead.	0	Dead.

## APPENDIX D: List of drugs that may have potential CYP3A4 interactions

### List of drugs that may have potential CYP3A4 interactions (source: ctep.cancer.gov) [Updated on May 1, 2007]

When drugs classified as ‘substrates’ are co-administered with lapatinib there is the potential for higher concentrations of the ‘substrate’. When lapatinib is co-administered with compounds classified as ‘inhibitors’, increased plasma concentrations of lapatinib is the potential outcome. The co-administration of ‘inducers’ would potentially lower plasma lapatinib concentrations. Only major substrates and effective inducers are listed.

#### CYP3A4 Substrates

Albuterol	Dihydroergotamine	Isradipine	Quinidine
Alfentanil	Diltiazem	Itraconazole	Rabeprazole
Alprazolam	Disopyramide	Ketamine	Ranolazine
Amiodarone	Docetaxel	Ketoconazole	Repaglinide
Amlodipine	Doxepin	Lansoprazole	Rifabutin
Amprenavir	Doxorubicin	Letrozole	Ritonavir
Aprepitant	Doxycycline	Levonorgestrel	Salmeterol
Aripiprazole	Efavirenz	Lidocaine	Saquinavir
Atazanavir	Eletriptan	Losartan	Sibutramine
Atorvastatin	Enalapril	Lovastatin	Sildenafil
Benzphetamine	Eplerenone	Medroxyprogesterone	Simvastatin
Bisoprolol	Ergoloid mesylates	Mefloquine	Sirolimus
Bortezomib	Ergonovine	Mestranol	Spiramycin
Bosentan	Ergotamine	Methadone	Sufentanil
Bromazepam	Erythromycin	Methylergonovine	Sunitinib
Bromocriptine	Escitalopram	Methysergide	Tacrolimus
Budesonide	Estradiol	Miconazole	Tamoxifen
Buprenorphine	Estrogens, conj., synthetic	Midazolam	Tamsulosin
Buspirone	Estrogens, conj., equine	Miglustat	Telithromycin
Busulfan	Estrogens, conj., esterified	Mirtazapine	Teniposide
Carbamazepine	Estrone	Modafinil	Tetracycline
Cerivastatin	Estropipate	Montelukast	Theophylline
Chlordiazepoxide	Ethynodiol estradiol	Moricizine	Tiagabine
Chloroquine	Ethosuximide	Nateglinide	Ticlopidine
Chlorpheniramine	Etoposide	Nefazodone	Tipranavir
Cilstostazol	Exemestane	Nelfinavir	Tolterodine
Cisapride	Felbamate	Nevirapine	Toremifene
Citalopram	Felodipine	Nicardipine	Trazodone
Clarithromycin	Fentanyl	Nifedipine	Triazolam
Clobazam	Flurazepam	Nimodipine	Trimethoprim
Clonazepam	Flutamide	Nisoldipine	Trimipramine
Clorazepate	Fluticasone	Norethindrone	Troleandomycin
Cocaine	Fosamprenavir	Norgestrel	Vardenafil
Colchicine	Gefitinib	Ondansetron	Venlafaxine
Conivaptan	Haloperidol	Paclitaxel	Verapamil
Cyclophosphamide	Ifosfamide	Pergolide	Vinblastine
Cyclosporine	Imatinib	Phencyclidine	Vincristine
Dantrolene	Indinavir	Pimozide	Vinorelbine
Dapsone	Irinotecan	Pipotiazine	Zolpidem
Dasatinib (1)	Isosorbide	Primaquine	Zonisamide
Delavirdine	Isosorbide dinitrate	Progesterone	Zopiclone
Diazepam	Isosorbide mononitrate	Quetiapine	

## CYP3A4 Inhibitors

Acetominophen	Diclofenac	Lomustine	Primaquine
Acetazolamide	Dihydroergotamine	Losartan	Progesterone
Amiodarone	Diltiazem	Lovastatin	Propofol
Amlodipine	Disulfiram	Mefloquine	Propoxyphene
Amprenavir	Docetaxel	Mestranol	Quinidine
Anastrozole	Doxorubicin	Methadone	Quinine
Aprepitant	Doxycycline	Methimazole	Quinupristin
Atazanavir	Drospirenone	Methoxsalen	Rabeprazole
Atorvastatin	Efavirenz	Methylprednisolone	Ranolazine
Azelastine	Enoxacin	Metronidazole	Risperidone
Azithromycin	Entacapone	Miconazole	Ritonavir
Betamethasone	Ergotamine	Midazolam	Saquinavir
Bortezomib	Erythromycin	Mifepristone	Selegiline
Bromocriptine	Ethinyl estradiol	Mirtazapine	Sertraline
Caffeine	Etoposide	Mitoxantrone	Sildenafil
Cerivastatin	Felodipine	Modafinil	Sirolimus
Chloramphenicol	Fentanyl	Nefazodone	Sulconazole
Chlorzoxazone	Fluconazole	Nelfinavir	Tacrolimus
Cimetidine	Fluoxetine	Nevirapine	Tamoxifen
Ciprofloxacin	Fluvastatin	Nicardipine	Telithromycin
Cisapride	Fluvoxamine	Nifedipine	Teniposide
Clarithromycin	Fosamprenavir	Nisoldipine	Testosterone
Clemastine	Glyburide	Nizatidine	Tetracycline
Clofazimine	Grapefruit juice (2)	Norfloxacin	Ticlopidine
Clotrimazole	Haloperidol	Olanzapine	Tranylcypromine
Clozapine	Hydralazine	Omeprazole	Trazodone
Cocaine	Ifosfamide	Orphenadrine	Troleandomycin
Conivaptan	Imatinib	Oxybutynin	Valproic acid
Cyclophosphamide	Indinavir	Paroxetine	Venlafaxine
Cyclosporine	Irbesartan	Pentamidine	Verapamil
Danazol	Isoniazid	Pergolide	Vinblastine
Dasatinib (1)	Isradipine	Phencyclidine	Vincristine
Delavirdine	Itraconazole	Pilocarpine	Vinorelbine
Desipramine	Ketoconazole	Pimozone	Voriconazole
Dexmedetomidine	Lansoprazole	Pravastatin	Zafirlukast
Diazepam	Lidocaine	Prednisolone	Ziprasidone

## CYP3A4 Inducers

Aminoglutethimide	Nevirapine	Phenytoin	Rifapentine
Carbamazepine	Oxcarbazepine	Primidone	St. John's wort (3)
Fosphenytoin	Pentobarbital	Rifabutin	
Nafcillin	Phenobarbital	Rifampin	

Note: Adapted from Cytochrome P450 Enzymes: Substrates, Inhibitors, and Inducers. In: Lacy CF, Armstrong LL, Goldman MP, Lance LL eds. Drug Information Handbook 15TH ed. Hudson, OH; LexiComp Inc. 2007: 1899-1912.

[figure not shown]
Only major substrates and effective inducers are listed.

Additional information for drug interactions with cytochrome P450 isoenzymes can be found at <http://medicine.iupui.edu/flockhart/>.

- (1) Investigator's Brochure: Dasatinib (BMS 354825). Bristol-Myers Squibb. October 2006.
- (2) Malhotra *et al.* (2001). Clin Pharmacol Ther. 69:14-23.
- (3) Mathijssen *et al.* (2002). J Natl Cancer Inst. 94:1247-1249.

Frye *et al.* (2004). Clin Pharmacol Ther. 76:323-329.

## APPENDIX E: LAPATINIB SCREENING SCHEMA

## APPENDIX F: Patient Medication Diary

### Appendix 7

### Patient Diary

Name:

take lapatinib - one pill twice daily - 1 hour before or after breakfast and dinner

Mon	Tue	Wed	Thu	Fri	Sat	Sun
12 morning [ ] evening [ ]	13 morning [ ] evening [ ]	14 morning [ ] evening [ ]	15 morning [ ] evening [ ]	16 morning [ ] evening [ ]	17 morning [ ] evening [ ]	18 morning [ ] evening [ ]
19 morning [ ] evening [ ]	20 morning [ ] evening [ ]	21 morning [ ] evening [ ]	22 morning [ ] evening [ ]	23 morning [ ] evening [ ] Lab Work RN will call	24 morning [ ] evening [ ]	25 morning [ ] evening [ ]
26 morning [ ] evening [ ]	27 morning [ ] evening [ ]	28 morning [ ] evening [ ]	29 morning [ ] evening [ ]	30 morning [ ] evening [ ]	1 morning [ ] evening [ ]	2 morning [ ] evening [ ]
3 morning [ ] evening [ ]	4 morning [ ] evening [ ]	5 morning [ ] evening [ ]	6 morning [ ] evening [ ]	7 morning [ ] evening [ ] Lab Work Clinic visit	8 morning [ ] evening [ ]	9 morning [ ] evening [ ]

List all symptoms whether or not you think they are related to the lapatinib	Dates	Treated at Home	Treated in doctor's office or Clinic	Hospitalized	Comments
Diarrhea					
Nausea					
Vomiting					
Other GI symptoms (describe)					
Skin rash (describe)					
Other symptoms					

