## 1. OBJECTIVES

### 1.1. Primary Objectives

- Determine the response rate to lapatinib administered as 500 mg orally twice daily on a continuous schedule in patients with metastatic melanoma harboring *ERBB4* mutations.

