## 5. TREATMENT PLAN

### 5.1 Lapatinib Administration

Treatment will be administered on an outpatient basis. Reported adverse events and potential risks are described in Section 7. Appropriate dose modifications lapatinib

are described in Section 5.2 below. No investigational or commercial agents or therapies other than those described below may be administered with the intent to treat the patient's malignancy.

Lapatinib will be administered as an oral dose of 500 mg twice daily (in the morning and evening). All medications are given daily for 28 days, 28 days (4 weeks) equals one cycle. The first course will consist of 28 days (one cycle). All subsequent courses will consist of 2 cycles. Up to 27 cycles may be administered (14 courses, approximately 2 years).

Patients will be instructed to take the medications at the same time each day taken one hour before or after meals. Patients will be advised not to consume grapefruit or grapefruit juice while taking the study medications. The patient will be requested to maintain a medication diary of each dose of medication and any side effects and/or adverse events the patient may experience. The medication diary will be returned to clinic staff at the end of each course.

Prior to discharge from the clinic, the research nurse will review the following information with the patient:

- The toxicities of each agent and how to treat/prevent them
- The signs and symptoms to report to the study team
- How to complete the medication self administration record (patient diary)(See Appendix F for lapatinib-specific medication diary).
- Instructions to carefully observe for signs and symptoms of AEs
- Potential risks regarding pregnancy and fetal exposure
- Study agents should never be shared

Patients will be dispensed 1 cycle of drug at a time (Section 5.3.7). At each cycle prior to drug dispensing, the toxicity information as described in section 7 will be reviewed with the patient.

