## 5.2 Dosing Delays/Modifications

General guidelines for treatment modifications at the time of re-treatment:

Adverse Events: All adverse events in this trial will be graded using the NCI Common Terminology Criteria for Adverse Events (CTCAE) version 4.0 - a complete listing is available at the CTEP website:  
<http://ctep.cancer.gov/forms/CTCAEv4.pdf>.

Dose adjustments will be made according to the guidelines below, with dose levels defined as follows:

Dose Level (DL)	Agent Dose
0	Lapatinib 500 mg twice daily
-1*	Lapatinib 1000 mg once daily

-2*	Lapatinib 750 mg once daily
-----	-----------------------------

\* The Cmax for lapatinib is higher when administered at a BID dose.

Please refer to Table 2 (background section) for specific values.

**Table 5** Summary of dose holding/interruptions and dose de-escalation recommendations for lapatinib in case of lapatinib-related adverse events (graded according to NCI-CTCAE v4.0)

General Adverse Events	Action
Non-hematological, Grade 1 or 2	Continue lapatinib therapy at full dose prescribed. Apply maximum supportive care recommendations. If prolonged duration of Grade 2 adverse event ( $\geq 7$ days) is affecting quality of life, decrease dose to DL -1, if symptoms persist and continue to affect quality of life for $\geq 7$ more days, a second dose reduction to DL -2 will be allowed.
Non-hematological, Grade 3 or 4 (excluding cardiac and hepatobiliary events)	Apply maximum supportive care recommendations. Hold lapatinib therapy until recovery to Grade $\leq 1$ (up to 14 days). For NCI-CTCAE v4.0 Grade 3 or 4 interstitial pneumonitis or Grade 4 rash manifested as toxic epidermal necrolysis (e.g. Stevens-Johnson Syndrome etc) lapatinib must be permanently discontinued If recurrence of adverse event after drug hold/interruptions is observed, and maximum supportive care measures applied, hold drug once again until recovery to Grade $\leq 1$ (up to 14 days) and restart drug at DL-1. If adverse event recurs, a second dose reduction to DL -2 will be allowed after symptoms recover to Grade $\leq 1$ .
Non-hematological, Grade 3 or 4 adverse events NOT resolved to Grade $\leq 1$ within a maximum of 2 weeks from last planned administration	Action (discontinue or resume lapatinib therapy) in individual cases after discussions with the Sponsor. Up to 2 reductions (DL-1 and DL-2) will be considered after maximum supportive care recommendations are introduced.
Cardiac Adverse Events	

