#### 5.3.2 Day 14 after the start of therapy (± 5 days):

- CBC with differential and platelet count
- Chem 14 Panel {Albumin, alkaline phosphatase, total bilirubin, Total CO2 (bicarbonate), Urea nitrogen (BUN), calcium, chloride (Cl), creatinine, glucose, potassium(K), total protein, SGOT [AST], SGPT [ALT], sodium(Na)}
- Clinic visit or phone interview by Research Nurse for review of systems.

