#### 5.3.3 At the end of Cycle 1 (after 28 days; ± 5 days):

- Physical examination
- CBC with differential and platelet count
- Chem 14 Panel {Albumin, alkaline phosphatase, total bilirubin, Total CO2 (bicarbonate), Urea nitrogen (BUN), calcium, chloride (Cl), creatinine, glucose, potassium(K), total protein, SGOT [AST], SGPT [ALT], sodium(Na)}
- Toxicity assessment, review of patient diary, and medication reconciliation
- Pregnancy counseling including the potential risk of fetal exposure, and verification of use of male and female contraception
- CT or MRI scan with oral and IV contrast (the same studies as those done at initiation of treatment should be performed)
- PK samples (patients who had PK samples performed prior to dose 1) - before 1st dose in the morning and 1h, 2h, 3h, 4h, 6h, 8h post morning dose.

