#### 5.3.7 Dispensing of medication

After reviewing the most recent lab data and the patient diary (please see sections 5.3.3, 5.3.5, and 5.3.6 above), and determining that the patient can continue with treatment, the physician or designee will contact the pharmacy and the investigational agent will be dispensed to the patient at the clinic visit. Only enough lapatinib for one (1) cycle of therapy + one week to allow for delays in appointment scheduling or travel may be provided to the patient each cycle. Patients will be required to return any unused study drugs or empty bottles to the NIH or participating institution at each clinic visit.

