### 8.1 Lapatinib (NSC 727989)

**Chemical Name:** N-{3-Chloro-4-[(3-fluorobenzyl)oxy]phenyl}-6-[5-(2-(methylsulfonyl)ethyl)amino]methyl-2-furyl-4-quinazolinamine

**Other Names:** GW572016, Tykerb®

**Molecular Formula:** C29H26ClFN4O4S(C7H8O3S)2H2O

**Molecular Weight:** 943.48

**Approximate solubility:** 0.007 mg/mL in water and 0.001 mg/mL in 0.1 N HCl at 25°C.

**Mode of Action:** Dual inhibitor of epidermal growth factor receptor (EGFR or ErbB1) and ErbB2 tyrosine kinases.

**How Supplied:** Lapatinib is supplied by the NCI/DCTD as 250 mg oval, biconvex, orange film-coated tablets with one side plain and the opposite side debossed with either FG HLS or GS XJG. The tablets contain 405 mg of lapatinib ditosylate monohydrate, equivalent to 250 mg lapatinib free base per tablet. The tablets are packaged into HDPE bottles with child-resistant closures containing 90 tablets per container.

Excipients present in the tablet include: Microcrystalline cellulose, povidone, sodium starch glycolate, and magnesium stearate.

The film-coat contains: Hydroxypropyl methylcellulose, titanium dioxide, macrogel/PEG 400, Polysorbate 80, FD&C Yellow No. 6, and FCF aluminum lake.

**Storage:** Store intact bottles at controlled room temperature (15°C-30°C). Protect from light.

**Stability:** Shelf life surveillance studies of the intact bottle are on-going. Current data indicates lapatinib is stable for at least 36 months at controlled room temperature (15°C - 30°C).

**Route of Administration:** Oral, taken one hour before or after meals.

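### The patient diary in Appendix F instructs half the protocol dose: one tablet twice daily, when the only tablet supplied is 250 mg and the dose is 500 mg twice daily

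*Combined protocol and SAP*

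**What the plan says.** The primary objective in Section 1.1 fixes the regimen under test: "Determine the response rate to lapatinib administered as 500 mg orally twice daily on a continuous schedule". The précis, the treatment schema, Section 5.1 and dose level 0 in Section 5.2 give the same dose. Section 5.2 allows two reductions: dose level -1 is 1,000 mg once daily and dose level -2 is "Lapatinib 750 mg once daily".

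Section 8.1 describes one product: "Lapatinib is supplied by the NCI/DCTD as 250 mg oval, biconvex, orange film-coated tablets". No 500 mg tablet appears anywhere in the document.

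The diary in Appendix F instructs the patient to "take lapatinib - one pill twice daily - 1 hour before or after breakfast and dinner". It prints morning and evening tick boxes for each day, with no strength in mg and no space for a tablet count. Section 5.1 refers to Appendix F as the lapatinib-specific diary and has the research nurse explain its completion before the patient leaves the clinic.

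The checks that could catch a dosing error are these:

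- Section 5.3.2 (day 14) lists laboratory tests and "Clinic visit or phone interview by Research Nurse for review of systems".
- Section 5.3.3 (end of cycle 1) lists "Toxicity assessment, review of patient diary, and medication reconciliation". Sections 5.3.5 and 5.3.6 repeat this later.
- Section 5.3.7 states: "Patients will be required to return any unused study drugs or empty bottles to the NIH or participating institution at each clinic visit".
- Section 8.4 requires drug accountability records.

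None of these gives the number of tablets expected.

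**The concern.** The diary is a written dosing instruction held by the patient, and it disagrees with the dose the trial is meant to test. A patient who follows it exactly takes half the intended dose and ticks every box, so the diary itself would show full adherence.

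Under Section 10.1.1, one cycle of therapy with re-evaluation makes a patient evaluable for response. Section 12.5.2 keeps patients with incorrect drug administration in the main response analysis. Under-dosed patients would therefore count among the 16 and 25 on which the two-stage rule in Section 12.1 operates, although the regimen they took is not the one named in the primary objective. They would also be patients with stage IV melanoma receiving half the intended treatment.

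The pharmacokinetic objective is less exposed. Only 10 patients are sampled (Section 5.4.1), and Appendix G records the dose with each sample. Those results would be distorted only if the sampled doses were themselves halved and the nominal dose was used in the analysis.

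**Working it through.** **Is 250 mg a misprint?** Section 8.1 says 405 mg of the ditosylate monohydrate equals 250 mg of free base. From the molecular formula there, the free base weighs 581.06 and the salt 943.47 (the plan states 943.48). Then 405 × 581.06 / 943.47 = 249.4 mg. The stated strength is reproduced.

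**Daily dose** = tablets per intake × 250 mg × intakes per day.

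| Regimen | Tablets per intake | Intakes per day | Tablets per day | mg per day |
|---|---|---|---|---|
| Protocol, dose level 0 | 500 / 250 = 2 | 2 | 4 | 1,000 |
| Dose level -1 | 1,000 / 250 = 4 | 1 | 4 | 1,000 |
| Dose level -2 | 750 / 250 = 3 | 1 | 3 | 750 |
| Diary as written | 1 | 2 | 2 | 500 |

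The diary dose is 500 / 1,000 = 50% of the protocol dose and 500 / 750 = 67% of dose level -2. Over a 28-day cycle it uses 2 × 28 = 56 tablets, against 4 × 28 = 112.

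**Would returned tablets show it?** Section 5.3.7 allows one cycle plus one week of drug. Assume this is dispensed at the protocol dose: 35 days × 4 = 140 tablets (the plan states no count). Tablets left are 140 − 4d at the protocol dose and 140 − 2d if the diary is followed:

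| Day d | Protocol dose | Diary dose |
|---|---|---|
| 14 | 84 | 112 |
| 23 | 48 | 94 |
| 28 | 28 | 84 |
| 33 | 8 | 74 |

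The gap is large enough to notice if someone counts and knows the expected number. The first visit at which reconciliation is listed is day 28 (± 5 days).

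**Effect on the primary result.** This cannot be computed, since no response rate at half dose is given. For orientation only, the exact binomial probability of a positive trial under the Section 12.1 rule (stop at 1 or fewer of 16; positive at 5 or more of 25) is 0.903 at a true response rate of 30%, 0.569 at 20% and 0.095 at 10%. Applying the lower rates to under-dosing would assume that every patient was under-dosed throughout and that response fell accordingly. Nothing in the conclusion rests on this.

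**The case against.** The mismatch itself is not in dispute. The best case for treating it as minor has four parts.

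1. *The page may be a sample.* It carries pre-printed dates and a stray appendix label, so it must be rewritten before use. That is fair, but a template passes its dosing line into every copy, and Section 5.1 names this one as the diary for the trial.

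2. *Other controls could catch it.* The nurse teaches the patient, unused drug is returned at each clinic visit, and a schema footnote has a physical examination every two weeks for the first three cycles, which suggests a visit near day 14. Section 8.1 also treats a dose as several tablets. The consent form is not in the text available, so it may give a tablet count. These points lower the chance that the error persists. They do not remove it: Section 5.3.2 permits a telephone call at day 14, the study calendar shows no physical examination then, and no available section gives a count to check against. If a label or consent form is correct, the patient holds two conflicting instructions.

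3. *Below dose level -2 in mg need not mean below it in exposure.* This stands. Section 2.2 reports that divided dosing roughly doubles steady-state AUC at the same total dose. Table 2 gives a geometric mean AUC of 18.1 h·mg/L at 500 mg twice daily, and 13.7 and 12.7 at 675 and 900 mg once daily. Assuming dose-proportionality, 250 mg twice daily would give about 18.1 over 24 hours if the tabled value covers 12 hours (2 × 18.1 / 2), or about 9 if it covers 24 hours (18.1 / 2). The first is above, and the second below, the roughly 13 expected at 750 mg once daily. The comparison with dose level -2 is therefore one of dose only.

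4. *Every other dosing section is right.* True, and no part of the statistical design is wrong. But the diary is the document the patient acts on.

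**Conclusion.** The concern holds. As written, the diary instructs 500 mg a day instead of 1,000 mg a day, a dose that matches no permitted level. This follows from the diary line, the single tablet strength and the stated dose, with no outside assumption. A patient following it could complete cycle 1 at half dose before the first listed reconciliation and would remain in the primary analysis.

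How many patients would be affected, and by how much the response rate would change, is unknown. The case for correction rests on the wrong dosing instruction alone, not on a projected loss of power. The returned-tablet figures assume 140 tablets dispensed per cycle.

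**What to change.** Change the Appendix F line to two 250 mg tablets (500 mg) twice daily. Provide matching versions for patients on reduced doses: four tablets (1,000 mg) once daily at dose level -1 and three tablets (750 mg) once daily at dose level -2. Both are once-daily regimens, so the morning and evening boxes need adapting as well.

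If the diary has already been issued, compare the doses actually taken with returned-tablet counts before the response analysis.

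The cost is a one-line correction to a one-page patient document and an IRB notification. Design, sample size and analysis are unchanged.
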